For surgeons who must operate in an irradiated field there are several challenges. There is often a delay from the conclusion of radiation and the planned local control surgery (often between 3-6 weeks) to allow for the skin and soft tissue to recover. Despite this delay there is often evidence of soft tissue damage with skin erythema, tissue edema, and desquamation frequently observed. With large and deep tumors there is often tension on the wound edges at closure and a large amount of dead space from tissue and tumor removal. This often manifests postoperatively as a seroma which can further delay wound healing. Many of these patients will need vascularized tissue transfer for wound closure after sarcoma resection [4, 5]. This has added morbidity to the patient.

Patients who develop wound complications have been shown to longer hospitalizations and higher costs. The utilization of preoperative external beam radiation has been shown to increase the risk of postoperative wound complications [1, 6]. Anatomic location of the tumor has also been shown to be a risk factor for the development of wound complications with lower extremities being higher risk than upper extremities. There are several published studies examining the effect of negative pressure wound therapy on high risk surgical wounds. Abdominal wound complications have been shown to be reduced with the use of incisional NPWT[7]. In the orthopaedic literature the use of negative pressure incisional dressings have been shown to lower the risk of wound complications in total hip arthroplasty, ankle surgery, acetabular fractures, and extremity fractures[8-12]. Other wounds have been treated effectively with NPWT with good results include sternotomy wounds[13], cardiac surgery[14],

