Enrollment of subjects from each institution will be centrally regulated through the primary center, The Medical University of South Carolina. Subjects will be accrued primarily through clinic referrals to a regional musculoskeletal oncologist for evaluation of soft tissue mass. Additionally subjects may be self-referred or present to a regional referral center's hospital or emergency department. The standard of care for these patients is after a tissue diagnosis is rendered showing the mass to be a soft tissue sarcoma and appropriate staging studies are complete that the patients will receive preoperative external beam radiation. After radiation (2-6 weeks) surgery is performed for local control. The investigative portion of the study will begin in the operating room after the surgical procedure is complete. Patients evaluated who meet the inclusion/exclusion criterion (see below) will be asked by study investigators whether or not they would like to participate in this study. Informed consent for participation in the study will take place in the clinic setting (often at the time of consent for surgery) after a biopsy has shown a sarcoma and the treatment plan is to include preoperative radiation and surgical excision (which would be the standard of care). Participation will be voluntary. Patients will be randomized before or at the time of surgery to receive standard dry gauze dressing or Prevena™ dressing.

Prior to or at the time of surgery the patients will be randomized to receive either a NPWT dressing or standard dry gauze dressing. This study is not amenable to blinding given the nature of dressing and the application by the surgeon. Randomization will be done by block randomization per site.

Compensation will not be provided to patients. Our goal is to obtain a total of 160 subjects with at least 6 month follow-up, approximately 75 subjects per treatment arm. (see sample size calculations)

Inclusion Criterion:

- Age>18
- Willing to consent to randomization and able to participate in the study
- Lower extremity or pelvic soft tissue sarcoma necessitating radiation prior to surgical resection
- Primary closure of wound
- Patients scheduled for surgical resection

Exclusion Criterion:

- Flap coverage or skin graft
- Patients scheduled for amputations as local control of their tumor
- Sarcomas where radiation is not planned preoperatively
- Repeat surgeries for oncologic reasons (positive margins)
- Known allergy to adhesive tape

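### Randomization may precede surgery although eligibility depends on primary closure, and no rule says when the assignment reaches the unblinded surgeon (minor)

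*Combined protocol and SAP*

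**What the plan says.** Section D gives the timing of randomization twice: "Patients will be randomized before or at the time of surgery to receive standard dry gauze dressing or Prevena™ dressing", and again "Prior to or at the time of surgery the patients will be randomized to receive either a NPWT dressing or standard dry gauze dressing". Neither sentence ties assignment to the state of the wound.

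The inclusion list contains "Primary closure of wound" and the exclusion list contains "Flap coverage or skin graft". Neither is qualified as planned or expected, whereas the amputation exclusion beside them refers to scheduled procedures. The criteria are first applied when consent is sought: "Patients evaluated who meet the inclusion/exclusion criterion (see below) will be asked by study investigators".

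Section D also says "The investigative portion of the study will begin in the operating room after the surgical procedure is complete". The Randomization paragraph keeps the list central and closed to the treating surgeon, blinds patients before the operation, and says surgeons cannot be blinded. The paragraph on tumor excision and limb reconstruction says the study does not alter surgical decisions and that the dressing goes on after the skin is closed.

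Section B, describing this kind of surgery in general, says "Many of these patients will need vascularized tissue transfer for wound closure after sarcoma resection" and, of large and deep tumors, "there is often tension on the wound edges at closure".

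Analytic Approaches estimates the proportion of patients with a wound complication in each group. It does not say which randomized patients are counted.

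**The concern.** If a patient is randomized before the operation and the wound is then closed with a flap or graft, that patient meets an exclusion criterion after assignment. Two things are left open. One is whether the surgeon knew the arm when choosing the closure. The other is whether the patient stays in the analysis.

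If the arm is known, closure or exclusion could depend on it. If patients are then dropped at different rates in the two arms, and their risk differs from that of the patients kept, the arms no longer represent the same population. The per-arm complication rates, which are the primary estimates, would shift by different amounts, and the secondary Fisher comparison would inherit the difference.

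Equal dropping in both arms, of similar patients, does not bias the comparison. It only restricts the population to primarily closed wounds.

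**Working it through.** **The plan's own figures.** Four sites × 40 = 160 patients, or 80 per arm. Less 5 inevaluable per arm, this gives 75. The 30% row of Table 3 reproduces with an exact (Clopper-Pearson) interval for 23/75 = 30.7%: 20.5% to 42.4%, half-width 10.9 points.

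**Does any text close the gap?**
- The list is closed to the surgeon. This hides the sequence, but does not say when an individual assignment is released.
- The dressing is applied after skin closure, and the investigative portion starts after the procedure. These time the dressing and the start of the study, not disclosure.
- Surgical decisions are said to be unaffected. This is a declaration with no concealment step stated behind it.
- Reading the criteria as planned closure would make the patient eligible at assignment, but an unplanned flap or graft would still have no stated handling.

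**Between-arm bias.** The documents give no rate of unplanned flap or graft, so every input here is assumed: 20% of wounds are high-risk with a 60% complication rate, the other 80% have a 25% rate, there is no true effect, and all excluded patients are high-risk. With a fraction f excluded, the rate among those left is

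rate(f) = [(0.20 − f) × 0.60 + 0.80 × 0.25] / (1 − f)

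| f | rate(f) |
|---|---|
| 0 | 0.320/1.00 = 32.0% |
| 5% | 0.290/0.95 = 30.5% |
| 8% | 0.272/0.92 = 29.6% |
| 10% | 0.260/0.90 = 28.9% |
| 12% | 0.248/0.88 = 28.2% |
| 15% | 0.230/0.85 = 27.1% |

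| Excluded, one arm vs the other | Spurious difference (points) |
|---|---|
| 10% vs 10% | 0 |
| 10% vs 8% | 0.7 |
| 12% vs 8% | 1.4 |
| 15% vs 5% (extreme) | 3.5 |

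Differences are taken before rounding.

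**Harsher variant.** Suppose the true rate is 30% in both arms and patients are dropped from one arm only: 5% to 15% of that arm, with a 40% to 60% complication rate. The remaining rate is (0.30 − d × p)/(1 − d), where d is the fraction dropped and p their rate. At the mild end, (0.30 − 0.05 × 0.40)/0.95 = 29.5%, a difference of 0.5 points. At the severe end, (0.30 − 0.15 × 0.60)/0.85 = 24.7%, a difference of 5.3 points.

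**Yardstick.** The Wald 95% half-width for a difference, with 75 per arm and 30% in both, is 1.96 × √(2 × 0.30 × 0.70/75) = 14.7 points.

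**Choice of denominator.** Under the first set of inputs, and if converted wounds keep the 60% risk, dropping rather than keeping these patients changes the per-arm rate by 32.0 − 30.5 = 1.5 points at 5% excluded and 32.0 − 28.9 = 3.1 points at 10%.

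**Precision.** If 5% or 10% of 80 (4 or 8 patients) were lost on top of the 5 allowed, n per arm would be 71 or 67. The exact half-width near 30% would be 11.1 (21/71) or 11.5 (20/67), against 10.9 planned.

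**The case against.** The strongest reply is that the bias needs a chain of events, none of which the documents report. An unplanned flap or graft must occur, the surgeon must know the arm before closure, a dressing assignment must influence the choice of closure or the decision to exclude, and patients must then be dropped at different rates. No direction is suggested either. The text leans the other way: surgical decisions are declared independent of the study, and the central list, the late start of the investigative portion and dressing after closure all fit disclosure at closure. This stands as an argument about likelihood. It does not supply the missing rule, because none of these statements fixes the release time.

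A reader might infer from Section B that intraoperative conversion to a flap will be common in this trial. The documents do not support that. The remark describes irradiated sarcoma surgery in general, may refer largely to patients whom screening removes, and gives no rate. Tension at the wound edges is not failure to close.

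It can also be said that the plan points to an evaluable-patient denominator, since it seeks 75 evaluable per group with at least six months of follow-up. In part it does, but what makes a patient inevaluable is not defined. Whether the main rate should cover all randomized patients or only primarily closed wounds is debatable; either is defensible if prespecified. That is why the analysis wording is secondary here.

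**Conclusion.** The point holds as a minor design weakness. The plan permits assignment before an eligibility condition that, for some patients, may be settled only in the operating room, and it sets no release time for an unblinded surgeon. That closure is sometimes settled so late is an inference.

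The likelihood of harm is unknown. Under the assumed risks, the between-arm bias is about 0 to 1.4 points, with 3.5 in an extreme case and 5.3 if patients are dropped from one arm only at the harshest inputs. All are small beside the 14.7-point yardstick, and the between-arm test is by the plan's own account neither primary nor adequately powered.

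A reader might go further and infer that surgeons will know the arm and choose closure accordingly, or that the reported rates will be biased. The documents support neither; they show only that nothing stated rules it out. Assigning once closure is confirmed is still the better rule: it settles this criterion first, and the documents name no benefit from assigning earlier.

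**What to change.** Replace both timing sentences in Section D with: *Patients will be randomized in the operating room, by release of the central assignment, after primary skin closure is confirmed.* Where a site must randomize earlier, add that the assignment stays sealed from the surgeon until closure is confirmed. This leaves every closure decision with the surgeon and agrees with the stated start of the investigative portion and with dressing after skin closure.

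As a secondary clarification, state in Analytic Approaches how any patient randomized earlier and then not closed primarily is counted. Report the complication rate both for all randomized patients by assigned arm and for primarily closed wounds.

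The cost is a change of text plus logistics: release during surgery (through REDCap or sealed envelopes) and both dressings available in the room at each site that would otherwise have randomized earlier. No patients or visits are added.

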Incisional negative pressure wound therapy for preoperatively irradiated pelvis and lower extremity soft tissue sarcoma wounds. A prospective, randomized pilot trial.

NCT02638298

Date Last Modified: April 21st, 2023

Principal investigator

[name]., MSCR

Associate [name]
Orthopaedic Oncology
Director of Orthopaedic Research
Associate Program Director
Medical University of South Carolina

[name]
[name]
[contact]
[contact]

Table of Contents

Hypothesis/Specific Aims.....	3
Background and Significance.....	3-5
Research Design.....	5-8
Methods.....	8-10
Budget.....	11-12
References.....	13

**Medical University of South Carolina
Protocol
PI Name: [name], MSCR**

Study Title: Incisional negative pressure wound therapy for preoperatively irradiated pelvis and lower extremity soft tissue sarcoma wounds. A prospective, randomized pilot trial.

A. HYPOTHESIS/SPECIFIC AIMS

The hypothesis of the proposed study is that use of a negative pressure wound therapy (NPWT) dressing on preoperatively radiated pelvic and lower extremity soft tissue sarcoma surgical wounds will significantly reduce the incidence and cost of wound complications.

This hypothesis will be tested through accomplishing the following specific aims:

- 1) Specific Aim 1- To estimate the wound complication rate of post-operative negative pressure dressings and traditional dry dressings, and risk of secondary interventions after resection of soft tissue sarcoma in lower extremities and the pelvis that have received pre-operative radiation. Wound complications are defined as a superficial infection, deep infection, need for prolonged (> 3 weeks) wound packing, or return to the operating room within six months for a secondary procedure. A secondary analysis of frequency and likelihood of antibiotic usage, pain scores, and functional scores will be analyzed in each group.
- 2) Specific Aim 2- To estimate the total cost of care and resource utilization in patients treated with negative pressure wound therapy and traditional dry dressings.

B. BACKGROUND AND SIGNIFICANCE

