- Recurrent soft tissue sarcoma

Consent:

Subjects will be consented for participation in the study by one of the aforementioned investigating surgeons (or research team) at the time of their evaluation in the clinic or hospital setting. Consent will include permission to randomize dressing to either to negative pressure wound therapy or “standard” dry gauze post-surgical dressing. Standardized study consent forms will be signed by the investigating surgeon and the patient. Standard surgical consent for the assigned procedure will be done in accordance with the standard of care.

Randomization:

Randomization will be predefined at each site using block randomization to ensure that each site is balanced for each arm of the study. This block randomization will be distributed and managed centrally at The Medical University of South Carolina. The randomization process will be performed centrally at MUSC and the treating surgeon will not have access to that randomization list. Preoperatively, the subjects will be blinded as to which dressing will be used for surgical wound coverage, but which dressing (i.e. which treatment arm) the patient was randomized to receive will be apparent postoperatively. Due to the design of the study, the surgeons are not able to be blinded.

Preoperative Evaluation:

Patients will receive the standard workup of a soft tissue sarcoma. The patient’s preoperative evaluation or treatment plan will not be affected by this investigation or the subjects desire to participate. Data collected preoperatively will include radiation type and dose, use of chemotherapy, VAS pain score, MSTS score, PROMIS Global Health score, medical comorbidities, tumor location, and any use of pain medicines.

Operative Intervention:

Surgery will be done in accordance with the standard of care for the excision of soft tissue sarcomas.

Anesthesia: Either regional or general anesthesia will be performed at the discretion of the treating physicians. Skin will be closed with either staples or 2-0 nylon sutures and a temporary closed suction drain may be placed. The use and duration of the drain will be at the surgeon’s discretion and in accordance with practice.

Tumor excision/limb reconstruction:

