Each patient will undergo the appropriate standard of care surgical procedure regardless of which treatment arm they are randomized to. This study will not affect any of the surgical decision making or surgical technique utilized. After skin closure from the surgical procedure patients will receive either a NPWT dressing or dry gauze dressing depending on the randomization.

Postoperative Care:

Postoperative care will be identical for both treatments. Wound care instructions will be given to both groups of study patients. Instructions for the control (dry gauze) group will be within the standard of care for each surgeon’s practice. Typically, a standard dressing care involves a dressing change at post-operative day two and then daily for the next week or until the wound is dry. Standardized instructions for the NPWT will be given in concordance with manufacturer’s recommendations. The NPWT dressing

would be typically discontinued on postoperative day 5-7 and standard dry gauze will be implemented at that point as needed. The Prevena™ device is FDA approved for use on incisions.

Physical therapy will be initiated prior to discharge, and continue either at home or as an outpatient, and continued at the discretion of the therapist and treating physician and in accordance with standard practice.

Postoperative Evaluations:

Formal wound and outcome assessments will take place at the 2 week, 6 week, 3 month and 6 month visits postoperatively or if patient presents for an unscheduled office visit with a wound complaint. Some information will be gathered from the medical record such as medication usage, information about the tumor from the pathology report, days in the hospital, treatment history of the tumor, and complications. Postoperative visits, and will include recording VAS pain levels, tumor size, margin status, length of hospitalization, use of pain medicines, and functional scoring. A wound assessment will be done as well.

Wound Assessment-

Direct assessment of each participant wound will be made during the specified follow up period at 2 weeks, 6 weeks, 3 months, and 6 months postoperatively.

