Risks Associated With NPWT Therapy/Dressing

Risks Due to PREVENA™ Incision Management System

Risks	Disorders/Conditions
Skin and Subcutaneous Tissue	
• Local cutaneous reaction (i.e. redness, rash, significant pruritis, urticaria)• allergic reaction• maceration• minor soft tissue damage• epidermal (skin) stripping• minor bleeding• pain• contusion (bruising)
Other	
• bleeding complications (associated with the surgical procedure, concomitant therapies and co-morbidities)• first degree burn (if device gets warm)• exposure related infection• localized infection• physical discomfort• minor desiccation (due to dressing leak)• moderate soft tissue damage (i.e. due to trip hazard, tubing entanglement)• deterioration of the wound (due to lack of visibility of incision site through dressing)

E. METHODS

Table 2

ASSESSMENT Provena™ 1 week duration	PRE-OP	2 WEEK POST OP VISIT	6 WEEK POST OP VIST	3 MONTH POST OP VISIT	6 MONTH POST OP VISIT
Wound assessment		X	X	X	X
Tumor size (cm)		X			
Type and Dose of Radiation	X				
Margin (+/-)		X			
Pain (VAS)	X	X	X	X	X
Hospitalization (days)		X			
Narcotic usage (+/-)	X	X	X	X	X
MSTS score			X	X	X
PROMIS Global Health	X			X	X

Other data collected to be analyzed for an association with wound complications or impact on treatment effect of Prevena™ (table 2)-

- 1) Surgery associated wound healing factors- prolonged (>3 wks) drainage, need for prolonged dressing changes or wound packing (>3 wks), return to OR, and use of antibiotics- All visits
- 2) Size of the tumor resected (cm)-2 week visit
- 3) Development of postoperative hematoma or seroma- All visits
- 4) Patient comorbidities- Smoking, peripheral vascular disease, BMI, diabetes, and MRSA status
- 5) Pain: The subject will be asked to record their current level of leg pain, and level of pain with leg use on a visual analogue scale (VAS) at all visits
- 6) Length of hospitalization (days)-2 week visit
- 7) Duration of narcotic usage (days)-All visits
- 8) Physical Function: The subject will be asked to complete a MSTS score, a validated patient survey for assessment of function at the 6 week, 12 week, and 6 month
- 9) Patient Global Assessment: The subject will be asked to complete a PROMIS Global Health forma validated patient survey for assessment of global musculoskeletal health and wellbeing at the preoperative visit, 3 month and 6 month visits.

Adverse Events:

Definitions

Adverse Event (AE).

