Analytic Approaches: To assess specific aim one patients will be followed longitudinally for the development of a wound complication and incidence of secondary procedures. Criteria for a wound complication are listed above. The data will be collected prospectively during routine follow up care of the patient and will include presence of absence of wound complication. The proportion of patients with a wound complication will be estimated and the 95% confidence for the true wound complication rate will be calculated with an exact binomial procedure. Although it is not the primary analysis, we will also compare the complication rates across the two groups using a Fisher's exact test (although the study is underpowered for this analysis). We will also use a logistic regression analysis where we adjust for center (using indicator variables) to estimate the overall wound complication rate in each group. For the risk of secondary interventions, the incidence of procedures performed for wound complications will be collected and multiple logistic regression analysis will be used to adjust these procedures in the incidence of wound complications.

To assess specific aim two the total cost of perioperative and post-operative care will be estimated from hospital billing records for patients. The median cost for the NPWT group and control group will be estimated and compared with independent t-test for normally distributed data and the Mann-Whitney test for any nonparametric data. A post hoc analysis of the cost of treatment for each arm will provide comparative effectiveness data for the use of NPWT in preoperatively radiated sarcoma surgical wounds. This is come directly from hospital and clinic charges, dressing and medication costs, and direct societal cost estimates from time missed from work.

Sample size justification: This is a pilot study with the primary objective of estimating complication rates in our patient population using NPWT and traditional dry dressings. We estimate that each of four institutions can enroll a least 40 patients over 36 months for a total of 160 patients. Assuming up to 5 patients in each group will have inevaluable data or follow-up, we plan on a total of 75 evaluable patients in each group. With 75 patients in each group and assuming complication rates of 10% to 30%, we have the following $\frac{1}{2}$ widths for 95% confidence intervals.

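### The resting pain score asks about the leg although pelvic sarcomas are eligible, so pelvic patients who answer literally do not report pain at the surgical site at rest

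*Combined protocol and SAP*

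**What the plan says.** The inclusion criteria in section D admit patients with "Lower extremity or pelvic soft tissue sarcoma necessitating radiation prior to surgical resection". The title, the hypothesis and Specific Aim 1 also name the pelvis.

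Specific Aim 1 makes pain a secondary outcome: "A secondary analysis of frequency and likelihood of antibiotic usage, pain scores, and functional scores will be analyzed in each group". The background lists better pain control as a possible benefit, and the device risk table lists pain and physical discomfort.

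The question itself is worded in one place only, section E, item 5: "The subject will be asked to record their current level of leg pain, and level of pain with leg use". That gives two scores, one at rest and one with activity. Elsewhere pain is named without a body site. Preoperative Evaluation lists "VAS pain score, MSTS score, PROMIS Global Health score, medical comorbidities, tumor location", Postoperative Evaluations "will include recording VAS pain levels, tumor size, margin status", and Table 2 has a single VAS pain row.

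The sample size justification states the trial's purpose: "This is a pilot study with the primary objective of estimating complication rates in our patient population using NPWT and traditional dry dressings".

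**The concern.** The dressing covers the incision, and in an eligible pelvic patient the incision may not be on the leg. Someone with a sore pelvic wound and a comfortable leg who takes the resting question at its word would score close to zero. The same question put to a leg-sarcoma patient takes in the operated region. The resting score therefore has a different meaning in the two anatomic groups, and the plan summarises pain by arm without separating them.

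Two uses of the score would suffer. A dressing effect on wound pain would be harder to see if pelvic patients' scores do not carry it. Section E also lists pain among the data to be examined for association with wound complications, and a leg score at rest is a weak marker of trouble in a pelvic wound.

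**Working it through.** **1. The passages side by side**

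| Place | Site or pain wording |
|---|---|
| Title, hypothesis, Aim 1, inclusion criteria | Lower extremity and pelvis |
| Section E, item 5, first score | Leg, current level |
| Section E, item 5, second score | Pain during use of the leg; location left open |
| Preoperative and Postoperative Evaluations, Table 2 | VAS pain, no site |

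Nothing outside item 5 supplies wording for the pelvis or the incision. The first score restricts where the pain is. The second restricts what the patient is doing, so a pelvic patient whose wound hurts on moving the leg can report it there.

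**2. The plan's own figure**

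The only design calculation is Table 3, which concerns complication rates. Arm size: (4 × 40 − 2 × 5) / 2 = 75, matching "we plan on a total of 75 evaluable patients in each group". Exact (Clopper–Pearson) 95% intervals for 8, 11, 15, 19 and 23 events in 75 have half-widths of 7.61, 8.59, 9.59, 10.35 and 10.93 points, against 7.6, 8.6, 9.6, 10.4 and 10.9 printed. The table reproduces to within rounding, and no pain quantity enters it.

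**3. Loss of a pain effect**

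Let Δ be the true difference between arms in surgical-site pain, taken as equal in pelvic and leg patients and fully captured in leg patients. Let f be the pelvic share and k the fraction of Δ that the item captures in pelvic patients. Then

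observed difference = (1 − f)Δ + f·k·Δ = Δ × [1 − f(1 − k)],

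so the proportional loss is f(1 − k). The documents give neither f nor k, so both are assumed. So is Δ = 10 mm.

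| f | k = 0 | k = 0.5 | k = 1 |
|---|---|---|---|
| 10% | loss 10%, 9 mm seen | loss 5%, 9.5 mm seen | none |
| 20% | loss 20%, 8 mm seen | loss 10%, 9 mm seen | none |
| 30% | loss 30%, 7 mm seen | loss 15%, 8.5 mm seen | none |

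The two scores may have different k. The at-rest score is the one where a low k is easier to argue.

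**4. What that would mean for sensitivity**

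The plan gives no pain test, effect size or standard deviation, so this is illustration only. Assume a two-sided 5% comparison of means, 75 per arm, unchanged spread, and a true effect of 0.46 SD (power 0.80).

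- f = 10%: with k = 0 the effect is 0.46 × 0.90 = 0.414 SD, power 0.72. With k = 0.5 it is 0.46 × 0.95 = 0.437 SD, power 0.76.
- f = 30%: with k = 0 the effect is 0.46 × 0.70 = 0.322 SD, power 0.51. With k = 0.5 it is 0.46 × 0.85 = 0.391 SD, power 0.67.
- k = 1: power stays at 0.80 for any f.

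**5. Direction between arms**

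Both arms get the same question, so the wording alone does not push the comparison toward either dressing. The stated allocation rule is "Randomization will be done by block randomization per site", with no stratification by tumor location. A chance difference in pelvic share could move mean pain between arms, but that is noise and not a systematic shift.

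**The case against.** A reader might infer that the pain outcome is invalid in pelvic patients, or that it dilutes any dressing effect on pain. The documents do not support either.

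- The second score does not confine pain to the leg. This stands, and it limits the clear mismatch to the resting score.
- The 10% to 30% loss is the k = 0 row alone. With k free, the loss can be zero. This stands.
- The affected analysis is lightly specified: a secondary description in each group of a pilot, with no between-arm pain test. The primary outcome and the sample size do not depend on it. This stands and keeps the point small.
- Nothing in the protocol defines the pain outcome as incision pain only. A complaint that leg patients may report pain from elsewhere in the limb would therefore be a preference. This stands, and the point does not rest on it.
- The patient form is not in the documents, and the leg wording may be loose drafting: section D also describes the trial population in extremity terms while admitting pelvic tumors. That is possible, but item 5 is the only instruction given, and followed as written it sends pelvic patients to the wrong site.
- Tumor location is collected, so pain can be split by site, and narcotic use is recorded at every visit without a body site. This helps in part. A split makes the pooling visible but cannot recover resting wound pain that was never asked about.

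**Conclusion.** The point holds as a minor mismatch between a stated measurement rule and the eligible population. For pelvic patients the resting question is directed away from the surgical site; for pain with leg use, the documents do not show how much pelvic wound pain is missed, if any.

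The consequence is some loss of sensitivity and of comparability between pelvic and leg patients in a secondary outcome. The size of the loss cannot be fixed from the documents. The ranges above rest on an assumed pelvic share, an assumed captured fraction and a common true effect in both anatomic groups. The primary complication-rate estimates and Table 3 are unaffected.

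**What to change.** Reword item 5 to ask for (a) current pain at the surgical site at rest and (b) pain at the surgical site with use of the leg or movement of the affected region. Use the tumor site as the reference at the preoperative visit. Table 2 could then show both scores in place of its single pain row.

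Flag any scores already collected under the old wording, and summarise pain by tumor location.

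The cost is an edit to one form item, with no added visit or assessor. The downside is that, if scoring has already begun (the documents do not state enrollment status), two wordings will coexist, possibly within the same patient across the five time points. The flag is needed so that they are not pooled unnoticed.
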